### Version History

Version	Changes Made	Date Finalized
1	Original Version based on Version 2.0 of Protocol	January 22, 2019
2	
Updated Version based on Version 3.0 of Protocol. Major changes include:
 
1. Section 2 was updated to reflect the new treatment regimen in Version 3.0 for both Cohort 1 and Cohort 2, sample size change in Cohort 1, number of dose-evaluable participants required for initial dose-finding evaluation (the first interim analysis), timing of the second interim analysis for opening Cohort 2 to study-naïve participants, and the new secondary objective for viral suppression in Cohort 1.
 
2. Section 3 was updated to include definitions of Evaluable Population, Cohort 2 Participants with Cohort 1 Experience, and Cohort 2 Participants without Cohort 1 Experience.
 
“Visits and Evaluation Schedule” was removed from Section 4 and put in the AIP, and the new secondary objective for viral suppression in cohort 1 was added in Section 4.
	September 3, 2020
3	
Updated Version based on Version 4.0 of Protocol.
 
Major changes include:
 
a. Removed references to Cohort 1 analyses. The primary analysis for Cohort 1 was performed using SAP Version 2.0.
 
b. Included all necessary changes from Protocol Version 3.0 to Version 4.0, including the modification of the study design of Cohort 2 to allow the oral lead-in phase to be an optional component of Cohort 2 study participation.
 
i. Modified Cohort 2 to include two groups: Cohort 2A (oral lead-in followed by injections) and Cohort 2B (direct to injections).
 
c. Restructured the SAP to include the following sections:
 
i. Overview of Sample Size Calculations
 
ii. Overview of Formal Interim Monitoring
 
iii. Outcome Measures
 
iv. Estimands and Analysis
 
v. Report Contents
	September 6, 2022
3.1	Minor Version change based on LOA #1. No changes needed.	August 25, 2023

## 1 Introduction

### 1.1 Purpose

This Primary Statistical Analysis Plan (SAP) describes the primary and secondary estimands that will address the Cohort 2 primary and secondary objectives of IMPAACT 2017. The Primary SAP includes general analytic approaches for all estimands and other outcome measures in the primary manuscript(s) or submitted to ClinicalTrials.gov (regardless of the reporting timeline). The Primary SAP facilitates discussion of the statistical analysis components among the lead study investigators and statisticians, helping them agree on the statistical analyses to be performed and presented in the primary analysis report.

It is noted here that all PK analyses, including those required to address the primary and secondary objectives of the study, will be done by the study pharmacologists based on a separate PK SAP (Version 2.0, dated 16 July 2022). In addition, the study's qualitative research team will do the analyses of the data collected through a single qualitative phone interview based on the Qualitative Analysis Plan.

Two primary safety analyses will be performed: (1) after the last participant in Cohort 1 has completed the Week 16 visit and (2) after the last participant in Cohort 2 (A/B) has completed 24/20 weeks on therapy. A secondary safety analysis will be performed after the last participant in Cohort 2 (A/B) has completed 48/44 weeks on therapy. Each primary safety analysis will be done after all queries have been resolved, and the study database closure/data lock has been completed. The primary safety analysis for Cohort 1 will be performed using Version 2.0 of the Primary SAP, dated 3 September 2020. This version of the Primary SAP will focus on the primary and secondary safety outcome measures for Cohort 2. Descriptions of analyses for other objectives and outcome measures not included in this Primary SAP will be provided in a separate SAP.

Detailed outlines of tables, figures, and coding descriptions that will be included in the Cohort 2 primary analysis report(s) are included in the Cohort 2 Analysis Implementation Plan(s) (AIP). As this study will support regulatory submissions, a separate regulatory AIP will be drafted for each regulatory submission.

### 1.2 Version History

The current Version 3.1 of the IMPAACT 2017 Primary SAP is based on protocol Version 4.0 and Letter of Amendment (LOA) #1.

Version 3.0 of the IMPAACT 2017 Primary SAP is based on protocol Version 4.0. The new version reflects all necessary changes from protocol Version 3.0 to Version 4.0, including the modification of the study design of Cohort 2 to allow the oral lead-in phase to be an optional component of Cohort 2 study participation. To accommodate this, Cohort 2 has been modified to include two groups: Cohort 2A (oral lead-in followed by injections) and Cohort 2B (direct to injections). In addition, references to Cohort 1 were removed, as the primary analysis for Cohort 1 will be performed using Version 2.0 of the Primary SAP. Details of the Cohort 1 primary analysis can be found in Version 2.0.

## 2 Study Overview

### 2.1 Overview of Study Design

IMPAACT 2017 is a Phase I/II, multi-center, open-label, non-comparative dose-finding study with the primary objective of evaluating the safety, acceptability, tolerability, and pharmacokinetics of oral cabotegravir (CAB) and long-acting injectable cabotegravir (CAB LA) as well as long-acting injectable rilpivirine (RPV LA) in virologically suppressed children and adolescents living with HIV-1 aged 12 to < 18 years.

The study design includes two cohorts of participants (Cohort 1 and Cohort 2) and five study steps. In Cohort 1 Step 1, participants received either oral CAB or oral RPV for at least 4 weeks and up to 6 weeks (maximum). In Cohort 1 Step 2, participants received injectable formulations of the study products, either CAB LA or RPV LA. Cohort 1 participants were assigned either CAB (Cohort 1C) or RPV (Cohort 1R) based on their pre-study cART regimen, and all participants continued their pre-study cART regimen during Cohort 1.

Cohort 2 participants discontinue their pre-study cART regimen and receive both study products, CAB and RPV, at the doses established in Cohort 1. Cohort 2 participants may enroll to either Cohort 2A to receive both oral CAB + oral RPV (Step 3) followed by both CAB LA + RPV LA (Step 4) or Cohort 2B to directly receive both CAB LA + RPV LA without an oral lead-in phase (Step 5). Unless otherwise specified, the term 'Cohort 2' applies to participants in both Cohort 2A and Cohort 2B.

Cohort 2 Treatment under Protocol Version 4.0:

- Cohort 2A (oral lead-in followed by injections): 30 mg CAB + 25 mg RPV once daily orally for at least four weeks, and up to a maximum of 6 weeks, during Step 3 oral phase, followed by intramuscular (IM) injections of CAB LA + RPV LA: first and second injections four weeks apart (CAB LA 600 mg injection + RPV LA 900 mg injection), with subsequent injections every eight weeks through and including Week 96 (CAB LA 600 mg injections + RPV LA 900 mg injections) during Step 4 injection phase.
- Cohort 2B (start with injections): IM injections of CAB LA + RPV LA: first and second injections four weeks apart (CAB LA 600 mg injection + RPV LA 900 mg injection), with subsequent injections every eight weeks through and including Week 92 (CAB LA 600 mg injections + RPV LA 900 mg injections) during Step 5 injection phase.

Participants who prematurely discontinue injectable study product permanently, will continue on-study for an additional 48 weeks after their last study product injection, per the long-term safety and washout PK follow-up (LSFU) schedule.

The sample size for Cohort 2 will be up to 155 adolescents in total. Up to 100 adolescents, who had not previously participated in Cohort 1 (i.e., Cohort 1-naïve), will be enrolled to achieve approximately 70 evaluable. Cohort 2A participants will receive the final recommended oral doses followed by the LA doses of CAB and RPV. Cohort 2B participants will receive the final recommended LA doses of CAB and RPV. Adolescents who participated in Cohort 1 (i.e., Cohort

1 rollovers; up to 55) may continue study participation in Cohort 2, if eligible, in addition to the up to 100 Cohort 2 participants newly enrolled to the study.

At the Week 96/92 visit, Cohort 2A Step 4 and Cohort 2B Step 5 participants continuing to receive injectable CAB LA + RPV LA external to the protocol will exit the study. Section 14.11 of protocol Version 4.0 has more information regarding post-trial access to study products. Participants who discontinue injectable CAB LA + RPV LA at the Week 96/92 visit will not exit the study. These participants will be followed for 48 weeks per the LSFU visit schedule.

## **2.2 Hypothesis**

Cohort 2: The selected dose of CAB LA and RPV LA, when given as dual therapy to stable, virologically suppressed adolescents living with HIV will maintain viral suppression and will be safe through Week 24 (for Cohort 2A oral followed by injectable) and through Week 20 (for Cohort 2B injectable only) in adolescents.

## **2.3 Study Objectives**

### **2.3.1 Primary Objective**

The primary objective for Cohort 2 (discontinuing a background cART regimen) is:

- 2.3.1.1 To assess the safety of CAB + RPV in adolescents living with HIV who are virologically suppressed through:
- Week 24 (Cohort 2A: oral followed by injectable);
  - Week 20 (Cohort 2B: injectable only).

### **2.3.2 Secondary Objectives**

The secondary objectives for Cohort 2 (discontinuing a background cART regimen) are:

- 2.3.2.1 To assess safety of CAB LA + RPV LA in adolescents living with HIV who are virologically suppressed through:
- Week 48 (Cohort 2A: oral followed by injectable);
  - Week 44 (Cohort 2B: injectable only).
- 2.3.2.2 To evaluate repeat-dose pharmacokinetics of CAB LA + RPV LA in adolescents living with HIV who are virologically suppressed through:
- Week 24 and through Week 48 (Cohort 2A: oral followed by injectable);
  - Week 20 and through Week 44 (Cohort 2B: injectable only).
- 2.3.2.3 To assess antiviral activity of CAB LA + RPV LA in adolescents living with HIV who are virologically suppressed through:
- Week 24 and through Week 48 (Cohort 2A: oral followed by injectable);
  - Week 20 and through Week 44 (Cohort 2B: injectable only).

## 2.4 Overview of Sample Size Considerations

Details of sample size considerations are provided in Section 9.4 of protocol Version 4.0. Briefly, the sample was driven primarily by safety considerations. **Table 1** below presents exact (Clopper-Pearson) 95% confidence intervals (CI) around various potential rates (0% and 20%) of Grade 3 or higher adverse events (AE) which might be observed in a total sample of 70 participants who enrolled directly into Cohort 2A or 2B (i.e., the primary analysis set for the Cohort 2 safety assessment) as well as for 100 participants who might contribute data to the safety analysis (i.e., all those exposed to the final recommended dose for Cohort 2).

**Table 1.** Percent of Participants Experiencing Grade 3 or Higher Adverse Events with Exact (Clopper-Pearson) 95% Confidence Intervals.

N	n (%) with Grade 3 or higher Adverse Events	95% CI
70	0 (0%)	0.00, 0.05
100	0 (0%)	0.00, 0.04
70	14 (20%)	0.11, 0.31
100	20 (20%)	0.13, 0.29

## 2.5 Overview of Formal Interim Monitoring

Interim Analysis #1 took place on 19 June 2020. Based upon study data from the first seven evaluable participants in each Cohort 1C and Cohort 1R, the IMPAACT 2017 CMC concluded that dosing regimens for oral CAB, CAB LA, and RPV LA achieved the PK targets as per protocol Version 2.0. Additionally, the LSFU PK results indicate both CAB and RPV concentrations maintain pharmacologically relevant concentrations, above the IC90, for several weeks after their final IM injection. This interim analysis confirmed that the doses implemented for both Cohort 1C and Cohort 1R passed the safety guidelines in Section 9.5.1.3 of protocol Version 2.0 for the first seven evaluable participants in each group. The CMC concluded that protocol criteria to open Cohort 2 to Cohort 1 graduates had been met, and the SMC agreed with this conclusion.

Interim Analysis #2 was conducted on 18 April 2022. The doses implemented for both Cohort 1C and Cohort 1R passed the safety guidelines per Section 9.5.1.3 of protocol Version 3.0. The CMC concluded that the analysis supported opening Cohort 2 accrual to participants who were not previously enrolled in Cohort 1, and the SMC agreed with this conclusion.

A final analysis of Cohort 1 data will be performed to confirm the final doses for Cohort 2 (using Version 2.0 of the Primary SAP).

## 3 Outcome Measures

### 3.1 Primary Outcome Measures

Safety through Week 24 (Cohort 2A)/through Week 20 (Cohort 2B):

- Any adverse event, regardless of grade
- Grade 3 or higher adverse event
- Grade 3 or higher adverse event assessed as related to study product(s)
- Serious adverse event meeting ICH criteria assessed as related to study product(s)
- Permanent discontinuation of study product due to adverse event assessed as related to study product(s)
- Death due to adverse event assessed as related to study product(s)

### **3.2 Secondary Safety and Viral Suppression Outcome Measures**

Safety through Week 48 (Cohort 2A)/through Week 44 (Cohort 2B):

- Any adverse event, regardless of grade
- Grade 3 or higher adverse event
- Grade 3 or higher adverse event assessed as related to study product(s)
- Serious adverse event meeting ICH criteria assessed as related to study product(s)
- Permanent discontinuation of study product due to adverse event assessed as related to study product(s)
- Death due to adverse events assessed as related to study product(s)

Virologic activity through Week 24 and through Week 48 (Cohort 2A)/through Week 20 and through Week 44 (Cohort 2B):

- Plasma HIV-1 RNA  $\geq 50$  copies/mL, per snapshot algorithm
- Plasma HIV-1 RNA  $\geq 200$  copies/mL, per snapshot algorithm

NOTE: PK outcome measures are described in the PK SAP.

## **4 Analysis Sets**

The following analysis sets are defined:

**All Treated:** All participants who took at least one dose of any study product in Cohort 2

**Evaluable:** For analysis purposes, evaluable participants will be defined as having been treated exclusively on the final recommended dose and either (1) having completed all treatment regimen through Week 24 (Cohort 2A)/Week 20 (Cohort 2B) or (2) having experienced any of the following:

- death that is attributable to the study product(s), OR
- study product-related Grade 3 or higher event (excluding injection-site AEs), OR
- permanently discontinued from treatment due to study product-related toxicities (regardless of grade) during these weeks of treatment.

Notes:

- An additional requirement for inclusion in the primary analyses for Cohort 2 is that the participants must be directly accrued to this cohort and be exclusively treated with the combination of the two study products; this will be approximately 70 participants.

- Oral bridging in Cohort 2 will not be counted as a substitute for an injection but as long as the recommended number of injections were given through Week 24/Week 20, even if they were out of window, the participant will be considered evaluable.

**Cohort 1 Rollover:** Cohort 2 participants who were previously enrolled to Cohort 1.

**Cohort 1-Naïve:** Cohort 2 participants who were enrolled directly to Cohort 2 without prior participation in Cohort 1.

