## 5 General Considerations

The derivation of PK parameters will be performed by the IMPAACT 2017 protocol pharmacologists, as described in the PK SAP. The statistical summaries to be prepared by the statisticians are described in this Primary SAP.

Continuous variables will be summarized by N, N missing, mean, standard deviation, and quantiles of minimum, 25th percentile, median, 75th percentile, and maximum. Categorical variables will be summarized by N (%) in each category, excluding the missing category in the denominator.

For all baseline demographics and exposure analyses, results will be presented for the All Treated analysis set. The baseline value will be the latest pre-dose assessment with a non-missing value, including those from unscheduled visits. If time is not collected, Day 1 assessments are assumed to be taken prior to first dose and used as baseline. Unless otherwise stated, if baseline data are missing, no derivation will be performed and baseline will be set to missing.

All safety data will be considered from the first patient exposure to study treatment. Each participant's safety data will be summarized as: (1) the worst grade of each AE and (2) the worst grade of each AE judged to be related to study treatment.

Listings of all Grade 3 or higher AEs regardless of treatment attribution, serious AEs meeting ICH criteria assessed as related to study product(s), and AEs which resulted in permanent discontinuation of study product(s) or death will be provided. These categories of AEs will also be summarized and broken down by System Organ Class. The Division of AIDS Table for Grading the Severity of Adult and Pediatric Adverse Events (DAIDS AE Grading Table), Corrected Version 2.1, dated July 2017, will be used in this study. This table is available on the RSC website at <https://rsc.niaid.nih.gov/clinical-research-sites/daids-adverse-event-grading-tables>.

Analyses of primary and secondary outcome measures will include Cohort 1-naïve evaluable participants, as defined above. Supplementary analyses of safety and virologic outcome measures will include all participants (Cohort 1-naïve and Cohort 1 rollovers) who received study products (All Treated analysis set referenced above).

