## 6 Estimands and Analysis

### 6.1 Primary Estimands and Analysis

Primary Objective 1: To assess the safety of CAB + RPV in adolescents living with HIV who are virologically suppressed through Week 24 (Cohort 2A)/Week 20 (Cohort 2B).	
Estimand	Probability of a virologically suppressed adolescent (aged 12 to <18 years) living with HIV-1, who was either exclusively treated with the combination of RPV and CAB at the final recommended dose for 24 weeks (for oral lead-in) or 20 weeks (for direct to injection), experienced a severe, potentially life-threatening, or death event attributable to CAB and/or RPV, or permanently discontinued CAB and/or RPV due to a related toxicity, having at least one event (any adverse event; severe, potentially life-threatening, or death event; severe, potentially life-threatening, or death event assessed as related to CAB and/or RPV; serious adverse event assessed as related to CAB and/or RPV; permanent discontinuation of CAB and/or RPV due to adverse event assessed as related to CAB and/or RPV; death due to adverse event assessed as related to CAB and/or RPV).
Treatment	30 mg CAB + 25 mg RPV once daily orally for four weeks followed by IM injections of 600 mg CAB LA + 900 mg RPV LA (first and second injections four weeks apart with subsequent injections every eight weeks) or direct to IM injections of 600 mg CAB LA + 900 mg RPV LA (first and second injections four weeks apart with subsequent injections every eight weeks).
Target population	Analysis set
Virologically suppressed children and adolescents 12 to <18 years of age living with HIV-1 exclusively treated with the combination of RPV and CAB at the final recommended dose for either 24 weeks (for oral lead-in) or 20 weeks (for direct to injection).	
Participants who are exclusively treated with the combination of RPV and CAB at the final recommended dose and either completed all treatment regimen through the Week 24 (Cohort 2A)/Week 20 (Cohort 2B) visit or experienced any of the following:
 

• death that is attributable to the study product(s), OR

• study product-related Grade 3 or higher adverse event (excluding injection-site AEs), OR

• permanent discontinuation from treatment due to study product-related toxicities (regardless of grade) during these weeks of

	treatment.
Variable(s)	Outcome measure(s)

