### Supplementary Analyses

Supplementary analyses for the primary outcome measures will include all participants (Cohort 1-naïve and Cohort 1 rollovers) who received study products. All intercurrent events will be addressed using a while on treatment strategy, and missing data will be handled using a complete case approach. Because this approach assumes data are missing completely at random, we will use multiple imputation that assumes missing at random as a sensitivity analysis. We will create 100 imputed data sets using appropriate FCS model and combine results using Rubin's rules. We will also present estimates assuming "best case" (i.e., probability of event = 0) and "worst case" (i.e., probability of event = 1) scenarios.

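### The evaluable set drops some related Grade 3+ injection-site reactions that the safety estimand and outcomes include

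*SAP*

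**What the plan says.** Section 5 of the SAP fixes the main population: "Analyses of primary and secondary outcome measures will include Cohort 1-naïve evaluable participants, as defined above". Section 4 gives two ways to be evaluable, both for participants treated exclusively on the final recommended dose. The first is completion: "having completed all treatment regimen through Week 24 (Cohort 2A)/Week 20 (Cohort 2B". The second is one of three events:

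- a death attributable to study product;
- a "study product-related Grade 3 or higher event (excluding injection-site AEs), OR"
- having "permanently discontinued from treatment due to study product-related toxicities (regardless of grade) during these weeks of treatment".

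Only the middle event carries an injection-site exclusion. The analysis-set cell in 6.1 repeats it: "study product-related Grade 3 or higher adverse event (excluding injection-site AEs), OR". The corresponding cells in 6.2.1 (Week 48/44 safety) and 6.2.2 (virology) do the same.

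The estimand row of the 6.1 table describes the same route as having "experienced a severe, potentially life-threatening, or death event attributable to CAB and/or RPV", with no injection-site exclusion. The estimand rows in 6.2.1 and 6.2.2 also lack one. The outcome lists in 3.1 and 3.2 include "Grade 3 or higher adverse event assessed as related to study product(s" and the all-cause Grade 3+ outcome, again without an exclusion.

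**The concern.** Evaluability decides who is in both the numerator and the denominator of the primary safety proportions. The outcome counts a related Grade 3+ injection-site reaction as an event, but that reaction does not by itself make a non-completer evaluable. Any other related Grade 3+ event would. Two participants with the same severity, attribution and follow-up are therefore treated differently according to where the event occurred.

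Cohort 2 treatment consists largely of repeated intramuscular injections, so the event type treated differently is specific to the route under study. The SAP gives no reason for the difference. At stake are a contradiction within each safety estimand table and a downward shift in the Grade 3+ and related Grade 3+ proportions relative to the estimand as written.

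**Working it through.** **1. The plan's own figures.** The exact limits are: lower = Beta quantile at 0.025 with parameters (x, n − x + 1); upper = Beta quantile at 0.975 with parameters (x + 1, n − x). For Table 1 in Section 2.4 this gives:

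| x/n | Recomputed | Table 1 |
|---|---|---|
| 0/70 | 0 to 0.0513 | 0.00, 0.05 |
| 0/100 | 0 to 0.0362 | 0.00, 0.04 |
| 14/70 | 0.1139 to 0.3127 | 0.11, 0.31 |
| 20/100 | 0.1267 to 0.2918 | 0.13, 0.29 |

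All four reproduce, so the interval method is not in question.

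**2. Who is lost.** Take a Cohort 1-naïve participant on the final dose with a related Grade 3+ injection-site reaction in the window.

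| What happens next | Evaluable under Section 4? | Within the estimand sentence? |
|---|---|---|
| Completes the regimen, even with injections out of window | Yes | Yes |
| Permanently discontinues, recorded as related toxicity | Yes | Yes |
| Does not complete, with another recorded reason (e.g. withdrawn consent, loss to follow-up, an injection never given) | **No** | Yes |

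Only the last row is affected.

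**3. Direction.** Restoring k such participants, each with an event, to x events among n changes the proportion by (x + k)/(n + k) − x/n = k(n − x)/[n(n + k)]. This is positive whenever x < n, so the exclusion can only lower the proportion relative to the stated estimand.

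**4. Size.** The SAP gives no rate of these reactions, so the counts here are assumed. The base of 70 is the evaluable target in Section 2.1.

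| Base | k = 0 | k = 1 restored | k = 3 restored |
|---|---|---|---|
| 0/70 | 0.0% (0.0 to 5.1) | 1/71 = 1.4% (0.0 to 7.6) | 3/73 = 4.1% (0.9 to 11.5) |
| 2/70 | 2.9% (0.3 to 9.9) | 3/71 = 4.2% (0.9 to 11.9) | 5/73 = 6.8% (2.3 to 15.3) |
| 14/70 | 20.0% (11.4 to 31.3) | 15/71 = 21.1% (12.3 to 32.4) | 17/73 = 23.3% (14.2 to 34.6) |

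Check for 2/70 with k = 1: 68/(70 × 71) = 0.0137, or 1.4 points.

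**5. How many to expect.** Section 2.1 enrols up to 100 naïve participants for about 70 evaluable, so at most about m = 30 are non-evaluable. Let r be the assumed share of them with a related Grade 3+ injection-site reaction. The expected loss is m × r, and the chance of at least one is 1 − (1 − r)^m.

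| m | r = 1% | r = 10% |
|---|---|---|
| 10 | 0.1 lost; chance 0.10 | 1.0 lost; chance 0.65 |
| 30 | 0.3 lost; chance 0.26 | 3.0 lost; chance 0.96 |

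**6. What deletion alone does.** Suppose 100 naïve participants are treated, 70 are evaluable with 2 related Grade 3+ events, and the non-completers not restored had none.

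| k | As written | Exclusion deleted | All treated naïve |
|---|---|---|---|
| 1 | 2/70 = 2.9% | 3/71 = 4.2% | 3/100 = 3.0% |
| 3 | 2/70 = 2.9% | 5/73 = 6.8% | 5/100 = 5.0% |

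With 80 treated instead of 100, k = 3 gives 5/80 = 6.3% against 6.8%. Deletion matches the stated estimand, but in these examples it overshoots the risk among everyone treated, because event-free non-completers stay out.

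**The case against.** The strongest reply is that little is lost and nothing is hidden. Participants recorded as stopping because of the reaction remain evaluable whatever its grade, and so do all completers. Section 4 also keeps anyone who received the recommended number of injections, even out of window. The supplementary analysis covers every primary outcome in a wider set: "Supplementary analyses for the primary outcome measures will include all participants (Cohort 1-naïve and Cohort 1 rollovers) who received study products". Section 5 adds listings of all Grade 3+ events regardless of attribution. The exclusion appears in the same form in four places, which suggests intent, and its rationale may lie in the protocol. Deleting it would also add outcome-dependent selection.

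Much of this stands. A reader might infer that the plan removes all severe injection-site reactions, or exactly those participants whom a reaction led to stop. Section 4 supports neither: the discontinuation route has no injection-site exclusion, so the loss depends on how the reason for stopping was recorded. A reader might also take three restored participants against two other events as typical. In the assumed ranges, an expected loss of three arises only with the maximum of 30 non-evaluable and a 10% rate.

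The remainder of the reply does not remove the point. A protocol rationale would not reconcile the estimand row with the analysis-set cell in the same table. The supplementary analysis pools up to 55 rollovers with the naïve participants. The missing-data sensitivity analyses in 6.1 stay within the evaluable set, and listings do not change the primary proportion. The selection argument is correct and bears on the remedy. Deletion could only add to the evaluable count, so it does not endanger the target of about 70.

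**Conclusion.** The inconsistency holds for the primary and secondary safety analyses. Relative to the estimand as written, the effect on the Grade 3+ and related Grade 3+ proportions is downward and probably small: about 0 to 3 participants, if 1% to 10% of 10 to 30 non-evaluable participants had such a reaction. One participant is worth about 1.4 points at a base of 2/70. These rates and counts are assumptions, since the SAP supplies none.

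Two stronger conclusions are not supported. The primary estimate is not necessarily far below the risk among all treated naïve participants: with one lost participant and 100 treated, it is 2.9% against 3.0%. Nor does the safety-bias argument carry over to the virologic analyses in 6.2.2, where the injection-site event is not the outcome. What remains there is a mismatch of wording.

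**What to change.** 1. Delete the bracketed injection-site exclusion from the evaluability definition in Section 4 as it applies to safety, and from the analysis-set cells of 6.1 and 6.2.1. Any related Grade 3+ event in the window then confers evaluability, as the estimand sentences already state.
2. Report the same safety outcomes, with exact 95% intervals, for all treated Cohort 1-naïve participants without rollovers. This shows the effect of admitting non-completers only when they had an event, without mixing in participants who had been in Cohort 1.
3. In 6.2.2, make the estimand row and the analysis-set cell agree on whether the exclusion applies.

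The cost is a short wording change and one extra table for the safety outcomes. The related Grade 3+ proportion may rise slightly. It should be read beside the all-treated naïve figure, because the deletion alone can overshoot.
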